#### 11.4.3 Urine Concentration Data

Urine PK samples will be collected for measurement of cytosine at the following time intervals during each study period: Pre-dose, 0-2h, 2-4h, 4-8h, 8-12h, 12-24h, 24-26h, 26-28h, 28-32h, 32-36h, 36-48h post-dose.

Cytosine concentrations in urine will be listed and summarised for each using the descriptive statistics N, n, arithmetic mean, arithmetic standard deviation (SD), coefficient of variation (CV%), minimum, median and maximum.

Urine concentrations will be listed using the Safety Set and summarised using the Urine Excretion Set. The summary may also be presented using the Safety Set if it differs from the Urine Excretion Set. All urine concentration data included in listings and summaries will be presented to three significant figures.

#### 11.4.4 Derived Urine PK Parameters

The derived urine pharmacokinetic parameters, Ae and Ae% (individual and cumulative), will be determined from the individual concentration versus time data using SAS version 9.3.

The derived urine PK parameter Ae will be calculated as: urine volume \* urine cytosine concentration. Ae% will be derived as:  $100 * Ae / Dose$  (where dose is expressed in ng). The cumulative parameters (CumAe, CumAe%) are the sum of the individual values calculated for each time interval from 0h to 48h. Total Ae0-48h is defined as the total amount excreted from 0 h to 48 h.

For the calculation of derived urine pharmacokinetic parameters, concentrations below the limit of quantification will be assigned a value of zero.

The derived urine parameters Ae, Ae%, CumAe and CumAe% for each time interval will be listed and summarised with the urine cytosine concentration data,

The derived urine pharmacokinetic parameters Total Ae0-48h and Total Ae0-48h% will be listed and summarised separately using the descriptive statistics N, n, arithmetic mean, arithmetic standard deviation (SD), coefficient of variation (CV%), minimum, median, maximum and geometric mean.

Urine PK parameter data listings will be presented using the Safety Set. Urine PK data summaries will be presented using the Urine Excretion Set and also the Safety Set should they differ. Urine PK parameter data included in listings and summaries will be presented to three significant figures with the exception of Ae% and CumAe% which will be presented to one decimal place.

#### 11.4.4.1 Statistical Analysis of Urine PK Parameters

Following logarithmic transformation, Total  $Ae_{0-48h}$  values will be subjected to an analysis of variance (ANOVA) including fixed effects for sequence (treatment schedule), period, treatment and subject nested within sequence. Point estimates and 90% confidence intervals (CI) will be constructed for the contrasts between fed and fasted states using the residual mean square error obtained from the ANOVA. The point and interval estimates will be back-transformed to give estimates of the ratios of the geometric least squares means (LSmean) and corresponding 90% CI. In addition, estimated geometric means will be presented.

The statistical analysis of the urine PK parameter will be performed using the Urine Excretion Set and also the Safety Set should they differ. Geometric LSmeans will be presented to three significant figures and the ratios and 90% CIs will be presented to 2 decimal places.

### 11.5 PD ANALYSES

Not applicable.

### 11.6 SAFETY ANALYSES

#### 11.6.1 Adverse Events

All AEs will be coded using the MedDRA dictionary using the version specified in the Data Management Plan (DMP).

All AEs, including those which occurred prior to the first dose of study drug, will be listed. Only treatment emergent adverse events (TEAEs), i.e., existing conditions that worsen or events that occur during the course of the study after administration of IMP, will be included within the summary tables. AEs occurring post-dose on Period 1 up to immediately prior to dosing on Period 2 will be assigned to the corresponding Period 1 treatment. Similarly, any AEs occurring post-dose on Period 2 up to Post-Study will be assigned to the corresponding Period 2 treatment. TEAEs will be summarised by treatment and overall.

An overall summary of AEs will be produced including the number of TEAEs; the number and % of subjects reporting at least 1 TEAE, serious TEAE (where SAE is reported as 'Yes'), TEAE leading to withdrawal from study drug (Action recorded as 'Study Drug Discontinued'); the number and % of subjects reporting TEAEs by severity and relationship to study drug. A subject with multiple occurrences of any AE is counted only once at the maximum level of severity or the highest association to study drug.

The number of TEAEs and the number and % of subjects reporting at least one TEAE will be tabulated by system organ class (SOC) and preferred term (PT). A subject reporting multiple episodes of a particular AE within a treatment period will only contribute one count towards the corresponding SOC and preferred term. The number of TEAEs and the number and % of subjects reporting at least one TEAE will also be tabulated by preferred term (PT), with the PTs sorted in descending order of frequency. A subject reporting multiple episodes of a particular AE within a treatment period will only contribute one count towards the corresponding PT.

In addition, the number and % of subjects reporting TEAEs will be tabulated by maximum severity and strongest relationship to study drug. For the summary of TEAEs by severity, if a subject has multiple events occurring within the same SOC or preferred term the event with the highest severity will be counted. Similarly, for TEAEs by relationship to study drug, if a subject has multiple events occurring within the same SOC or PT, the event with the highest association to study drug will be counted.

Data will be listed by treatment. For any adverse event taken prior to first administration of study drug, treatment will be described as 'Prior to Treatment'.

Where there are only partial dates/times recorded for adverse events, adverse events will be assigned to treatment unless it can be ruled out based on the partial information.

The derived variables, 'Time from Dose' and 'Duration' will be presented where full date and time are present. If partial dates are present for any parameter required in the calculation, then the variable will not be populated. The following will be used to calculate the variables:

**Duration:** (Date/Time of Resolution-Date/Time of Onset) + 1 minute;

**Time from Dose:** (Date/Time of Onset-Date/Time of Start of Dose).

The following will be presented in listing format within the data summaries:

Serious Adverse Events – If there are none present, the listing will be produced stating: '*No subjects experienced any serious adverse events*'.

Adverse Events which Led to Withdrawal of Study Drug – If there are none present, the listing will be produced stating: '*No subjects experienced any adverse events that led to withdrawal of study drug*'.

Adverse event data will be summarised and listed using the Safety Set.

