4.2. Secondary Objectives

[figure not shown]
1. To compare the AUC_{0-t} , $T_{1/2}$ and T_{max} of cytisine in subjects under fed and fasted conditions, following administration of 3 mg cytisine (2 x 1.5 mg cytisine tablets).
2. To assess the safety and tolerability of cytisine in a new formulation at the 3 mg dose level under fed and fasted conditions.

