11. STUDY PROCEDURES

All subjects will be evaluated for inclusion in the study during the Screening Period. Subjects who are eligible for the study will be randomized according to the randomization schedule. Subjects will receive their study medications on Day 1 and Day 3 of the 5-day clinic stay followed by the required blood and urine samples. The subjects will be released from the clinical research facility after the last PK and urine sample is collected and safety assessments completed on Day 5. All subjects are required to complete a telephone follow-up on Day 6-8 days post last dose.

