11.2.5. Day 3 (Period 2)

The following study procedures are to be performed prior to dosing:

1. Remaining blood and urine samples to complete Period 1 (through 48 h) pharmacokinetics will be collected (Sections 12.1 and Section 12.2).
2. Pre-dose blood draw and urine for PK to be taken within 60 minutes prior to dosing.
3. Vital signs (supine blood pressure, pulse rate and oral temperature) will be recorded at pre-dose and again approximately 2 hours after administration. Any clinically relevant changes should be documented as adverse events.
4. Administration of cytisine according to randomization:

Schedule A (6 subjects):

Cytisine (2 x 1.5 mg tablets) will be administered after the overnight fast of at least 10 hours and subject will continue fasting until lunch (*fasting state*). Dosing will be administered with 240 mL (8 fluid ounces) water. Except for fluids taken for dosing, no fluids will be allowed from 1 hour before dosing until 1 hour post-dosing.

Schedule B (6 subjects):

Cytisine (2 x 1.5 mg tablets) will be administered 30 minutes after the start of a high fat breakfast (*fed state*) with 240 mL (8 fluid ounces) water. No additional fluids are to be taken until 1 hour post-dosing

1. Document concomitant medications and any adverse events.
2. Collect plasma sample for PK analysis
3. Collect urine sample for PK analysis.

All subjects will remain in the clinic overnight.

11.2.6. Day 4

Blood and urine samples for pharmacokinetics in Period 2 will be collected (Section 12.1).

1. Document concomitant medications and any adverse events.
2. Collect plasma samples for PK analysis
3. Collect urine samples for PK analysis.

All subjects will remain in the clinic overnight.

11.2.7. Day 5

Remaining blood and urine samples for pharmacokinetics in Period 2 will be collected (Sections 12.1 and 12.2).

1. Document concomitant medications and any adverse events.
2. At 48 hours post-dosing, collect blood for haematology and biochemistry and collect urine for urinalysis.
3. Obtain 12-lead ECG (in triplicate) similar to what was done at screen and review prior to discharge.

Upon final review by the study physician, the subject will be released from the clinical research facility.

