15.8.3. Adverse Events

AEs will be tabulated and summarised according to the MedDRA version 20.0 or higher, and classified by system organ class (SOC) and preferred term (PT). The following information recorded or computed is used for the description of the adverse events: reported Term; SOC and PT by MedDRA coding; onset date, onset time, offset date and offset time; seriousness; severity (intensity); relationship (causality); action taken; outcome.

Treatment-emergent adverse events (TEAEs) are defined as AEs not present prior to first administration of investigational product, or AEs present before first administration of investigational product that worsen after the subject receives the first dose of investigational product. TEAEs that occur after administration of investigational product in a given period are assigned to the treatment administered in that period. A separate listing of SAEs will be presented, if applicable.

Frequencies of TEAEs will be presented by SOC and PT, severity and relationship, by Fed/Fasting regimens and overall.

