15.8.4. Safety Laboratory tests

Biochemistry, haematology and urinalysis parameters will be listed with any out of normal/alert range values flagged. Laboratory test results which are out of normal range will also be presented separately along with normal reference ranges.

Abnormalities in clinical laboratory tests will be classified in terms of clinical significance. Clinically significant abnormalities will be reported as AEs.

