### 11.6.2 Laboratory Data

Routine safety laboratory tests will be carried out at Screening and Day 5.

The safety laboratory parameters required for this study are listed in section 9.1.1.

Safety laboratory data listings will be presented in two ways:

- Out of range values - any values that fall outside of the normal/alert ranges (presented in listing format within the data summaries)
- All safety laboratory data (including physician's review (Normal, Abnormal-NCS, Abnormal-CS)) with any out of range values flagged (presented within the data listings).

Microscopy, virology, urine drugs of abuse and alcohol screen, pregnancy tests and other parameters will also be listed.

If there are no further parameters databased other than those specified in section 9.1.1 then the 'Other Laboratory Data' listings should display, '*No other laboratory parameters to report*'.

Laboratory data will be listed using the Safety Set.

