### 11.6.4 Electrocardiogram

#### 11.6.4.1 12-Lead ECG

12-lead ECGs will be performed in triplicate at Screening and prior to discharge on Day 5.

12-lead ECG parameters (heart rate, PR interval, QRS width, QT interval and QTcF interval) will be listed with any out of normal range values (see Appendix 16.1) flagged (flag 'H' or 'L' appended to relevant result). The ECG results will also be assessed as either 'normal' or 'abnormal' with comments on abnormal results also presented.

12-lead ECG data will be listed using the Safety Set.

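### Labs, urinalysis and ECG are repeated only on Day 5, after both doses, so an AE first detected there cannot be attributed to fed or fasted, yet SAP 11.6.1 would book it to the Period 2 regimen

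*SAP*

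**What the plan says.** **Objective.** Protocol 4.2, second secondary objective: "To assess the safety and tolerability of cytisine in a new formulation at the 3 mg dose level under fed and fasted conditions".

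**Dosing.** Protocol 11: "Subjects will receive their study medications on Day 1 and Day 3 of the 5-day clinic stay", one regimen on each day. Schedule A is fed then fasted; Schedule B is fasted then fed (SAP 3.6).

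**Assessments.** SAP 11.6.2: "Routine safety laboratory tests will be carried out at Screening and Day 5". SAP 11.6.4.1: "12-lead ECGs will be performed in triplicate at Screening and prior to discharge on Day 5". Protocol 11.2.7, on Day 5: "At 48 hours post-dosing, collect blood for haematology and biochemistry and collect urine for urinalysis". Protocol Table 5 and SAP 3.4 show the same two time points.

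**From finding to AE.** Protocol 15.8.4, on laboratory tests: "Clinically significant abnormalities will be reported as AEs". Protocol 13.7 and 15.8.1 provide the same for ECGs.

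**From AE to regimen.** AEs after the first dose and before the second go to the Period 1 regimen; after that, "any AEs occurring post-dose on Period 2 up to Post-Study will be assigned to the corresponding Period 2 treatment" (SAP 11.6.1). Protocol 15.8.3 likewise assigns by the period in which the event occurs, and then: "Frequencies of TEAEs will be presented by SOC and PT, severity and relationship, by Fed/Fasting regimens and overall".

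**The concern.** The by-regimen TEAE tables serve the objective on safety under fed and under fasted conditions. They look like a within-subject comparison in which each subject contributes to both columns. For an abnormality first found by the planned Day 5 labs or ECG, the design cannot supply that comparison. No planned lab or ECG falls between the two doses, so nothing shows whether the abnormality began after Dose 1 or after Dose 2. The previous planned value is from Screening, up to 28 days before the first dose, so even onset after dosing is not observed.

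If the event is dated at detection, the attribution rule still gives it a regimen. A reader of the table could then take a fed or fasted laboratory or ECG signal, or its absence, as evidence about food when it only records which dose came second.

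**Working it through.** The plan states no figure on this point, so there is none to reproduce. The check sets the timing against the attribution rule.

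**1. Timing**

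| Assessment | Planned times | Separates the two doses? |
|---|---|---|
| Haematology, biochemistry, urinalysis | Screening, Day 5 (48 h after Dose 2, about 96 h after Dose 1) | No |
| 12-lead ECG | Screening, Day 5 before discharge | No |
| Vital signs | Screening, Day 0, before and 2 h after each dose, Day 5 | Yes |

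**2. Is there already a rule for unobserved onset?** SAP 11.6.1 has a rule for partial dates and times. It concerns incomplete records. A Day 5 finding has a complete detection date, so that rule does not reach it. Protocol 13.2.2 collects onset date and time, and neither document says how to date an abnormality that began in an unobserved interval.

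**3. Where a Day 5 finding lands if dated at detection.** With 6 subjects per schedule, all 6 in Schedule A are booked as fasted and all 6 in Schedule B as fed.

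**4. Effect on a true difference.** As an illustration, assume an abnormality arises only after the fed dose, at rate 1/6, and persists to Day 5.
- True split: 12 × 1/6 = 2 fed and 0 fasted.
- Booked fed (Schedule B, fed second): 6 × 1/6 = 1.
- Booked fasted (Schedule A, fed first): 6 × 1/6 = 1.

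More generally, let rF and rS be the event rates after the fed and fasted doses, and let p be the chance that a Dose 1 effect is still present on Day 5, taking every Dose 2 effect as present. Ignoring subjects with two events, expected counts are:
- booked fed = 6 × (rF + p × rS)
- booked fasted = 6 × (rS + p × rF)
- difference = 6 × (1 − p) × (rF − rS)

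The difference shrinks as p rises and vanishes at p = 1. It does not reverse sign, so the distortion is dilution and does not systematically favour one regimen.

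**5. Share misbooked.** If a share q of these AEs truly began after Dose 1 and before Dose 2, a share q is in the wrong column. The documents do not give q. Over q = 0 to 1 the share runs from 0% to 100%.

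**6. Percentages.** One event prints as 1/12 = 8.3% if the denominator is everyone dosed under that regimen. Only 6 subjects could contribute such an event to that column: 1/6 = 16.7%. Both figures require onset dated at detection, and the 8.3% also requires that denominator. The table shells are redacted, so the denominator cannot be confirmed.

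**7. The Day 2 reference.** Protocol 13.1 speaks of recording laboratory changes from screening seen on Day 2. Table 5, Section 11.2.4 (Day 2) and Section 13.4.1 place no labs on that day. The blood volume table in Section 14 does not allow for them either: 4.5 + 4.5 + 2.7 + 2.7 + 97.2 = 111.6 mL, which is one Screening and one Day 5 draw for each panel plus PK. (The sample-number column prints 2 in the Day 5 rows, but the volume charged there is that of one draw.)

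**The case against.** Several points on the other side stand.

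- **The booking may be right.** Dose 2 is the more recent exposure. A reader might infer that the by-regimen tables are wrong for these events, or that Dose 1 is as likely a cause as Dose 2. No statement in either document supports that.
- **Half-life settles nothing.** A reader might argue that so little drug remains on Day 5 that timing gives no reason to prefer Period 2. At 4.8 h, 2^(−48/4.8) = 0.098% of Dose 2 remains. But Dose 1 is 48 h older: 2^(−96/4.8) is about 0.0001%, roughly 1/1,000 as much. Residual drug, if it pointed anywhere, would point to Dose 2. A persisting effect that began in Period 1 can be neither shown nor excluded this way.
- **Misassignment of first-dose events is not certain.** Assignment follows recorded onset, and Protocol 13.1 allows any safety procedure at any time. A symptom or unscheduled test can properly place an event in Period 1. Only clinically significant, treatment-emergent findings enter the tables.
- **No formal fed/fasted lab or ECG comparison is planned.** Values are listed, not summarised by regimen, and the AE listing's time from dose would show an event dated about 48 h after Dose 2.
- **The attribution rule is the same in both documents**, so a special category departs from both.

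These points limit the size of the problem and the wording of the conclusion. They do not supply a rule for an abnormality with a complete Day 5 detection date and an unobserved onset, and the TEAE tables by regimen would still print it under Fed or Fasted.

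**Conclusion.** The concern holds in a limited form. A clinically significant abnormality first detected by the Day 5 labs, urinalysis or ECG cannot be attributed to the fed or the fasted dose. If it is dated at detection, the SAP counts it under the Period 2 regimen, so for these events the columns reproduce sequence and would dilute a real difference. The documents support calling the attribution unverifiable. They do not support calling it wrong, and they give no estimate of the share misbooked.

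Severity is minor. Only AEs detected by labs or ECG, in the by-regimen TEAE tables, are touched. Overall totals, symptomatic AEs, vital signs and the primary PK analysis are unaffected. The conclusion assumes onset is recorded at detection, no unscheduled test between the doses, and subjects who received both doses. The dilution result also assumes sequences balanced 6 and 6 and the same persistence for first-dose effects in both schedules.

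**What to change.** - **SAP 11.6.1:** add that AEs identified only from the Day 5 laboratory, urinalysis or ECG assessments are tabulated under Overall, in a row marked as not attributable to a regimen, and not under Fed or Fasted, unless a symptom or an unscheduled assessment dates onset to one period. Keep the Period 2 booking visible in the AE listing.
- **SAP 1.2:** record this as a change from Protocol 15.8.3.
- **SAP 11.6.2 and 11.6.4.1:** state that no fed/fasted conclusion is drawn from the Day 5 labs or ECG. The fed/fasted safety statement then rests on AEs with a dated onset and on the vital signs taken around each dose.
- **Protocol 13.1:** reconcile the reference to Day 2 laboratory changes with the schedule.

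The cost is SAP wording and one extra row in the TEAE tables, with no added procedures or subjects. The downside is that a few events leave the regimen columns; overall totals do not change. The change does not resolve whether such an abnormality began before dosing, since the only earlier planned value is still the Screening one.

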### 11.6.2 Laboratory Data

Routine safety laboratory tests will be carried out at Screening and Day 5.

The safety laboratory parameters required for this study are listed in section 9.1.1.

Safety laboratory data listings will be presented in two ways:

- Out of range values - any values that fall outside of the normal/alert ranges (presented in listing format within the data summaries)
- All safety laboratory data (including physician's review (Normal, Abnormal-NCS, Abnormal-CS)) with any out of range values flagged (presented within the data listings).

Microscopy, virology, urine drugs of abuse and alcohol screen, pregnancy tests and other parameters will also be listed.

If there are no further parameters databased other than those specified in section 9.1.1 then the 'Other Laboratory Data' listings should display, '*No other laboratory parameters to report*'.

Laboratory data will be listed using the Safety Set.

### 11.6.3 Vital Signs

Vital signs will be taken at Screening; Day 0; Day 1 at pre-dose and 2h post-dose (Period 1); Day 3 at pre-dose and 2h post-dose (Period 2); Day 5.

Vital signs parameters (supine systolic and diastolic blood pressure and pulse rate and oral temperature) will be listed with any out of normal range values (see Appendix 16.1) flagged (flag 'H' or 'L' appended to relevant result). Descriptive statistics (N, n, mean, SD, minimum, median and maximum) of absolute and change from pre-dose to 2 h post-dose will be tabulated by treatment.

Vital signs data will be listed and summarised using the Safety Set.

